## **DAPPER Protocol**

### **Inclusion/Exclusion Criteria**

Inclusion criteria: 1) self-reported pain  $\geq 3$  out of a 0 -10 scale that has lasted longer than 3 months and keeps them from doing at least one activity that they would like, 2) Self-Identify as African American/Black female 3) non-institutionalized and living in the community Maryland, Virginia or Washington DC area. 4) score a 5 or higher on the PHQ9 (depression measure) at least two times during a two week period (screening call and then at first data collection visit via video), 5) pre-frail ( one or two criteria on frailty phenotype) or frail (three or more of the criteria on frailty phenotype), 6) at least one ADL or IADL limitation Exclusion Criteria: 1) Hospitalized  $> 3$  times in the last year, 2) participating in physical therapy, 3) have a terminal diagnosis ( $< 1$  year expected survival), 4)  $\geq$  moderate intellectual impairment (5-7 errors) based on the Short Portable Mental Status Questionnaire (SPMSQ), 5) Unable to understand or speak English

We will recruit participants from the PI's Communication Behaviors and Development of Pain and Depression Intervention among Older African American Women (IRB000170533) study. This study consisted of focus groups for the development of the DAPPER intervention. We will only contact participants who agreed to be contacted for future studies. We will contact these participants by phone and ask them if they are interested in participating in the intervention (please see the phone script). If participants agree to this, we will screen them on the phone at this time.

Recruitment will also be conducted via mass marketing. A study team member will identify organizations (e.g. churches, senior high rises) that have established partnerships with the Johns Hopkins School of Nursing Center of Innovative Care in Aging, the Johns Hopkins Center for Health and Aging, and the Johns Hopkins Geriatric Services Frailty registry. The study team will provide each site (Maryland AARP, senior high rises, African American hair salons, etc.) director with flyers. We will send the flyers via email to distribute on social media sites or distribute to mailing lists. We will send messages through Johns Hopkins MyChart for recruiting to patients who have demographics that match the study inclusion criteria. We will not send recruitment messages to individuals who have opted out of receiving them. We will also provide flyers to health care providers of older adults and/or chronic pain patients. We will also use "Word of Mouth" campaigns – volunteers & ambassadors, clinics, and personal contacts. The potential participants will be instructed to contact the research team if they are interested in participating in the research study. A study team member will screen the potential participant and explain the study over the phone. If the individual is eligible a study team member will arrange a video visit to re-screen, explain the study again, ask the participant understanding of the study, and give them an opportunity to ask questions. If the potential subject wishes to participate, the study team member will obtain consent either

by delivering the consents as a hard copy or via DocuSign and conduct the baseline questionnaire. If participants do not do a Docusign consent we will use the following process:

- After the consent designee and participant or LAR review the consent form, the participant or LAR is offered the opportunity to ask any questions and have those questions answered.
- The participant (or LAR) will sign and date/time the paper copy of the informed consent document.
- The consent designee must verify the participant or LAR physically signed the consent document either by viewing via video conference, obtaining a photo of the complete signed consent document; or obtaining verbal confirmation from the participant that she signed the consent form or agreed to participate electronically.
- The signed document is then mailed, emailed, photo/scanned to text or faxed to the consent designee.
- If the signed consent is provided as an electronic copy (dropped off at their place of residence) emailed ,photo/scanned to text, or faxed), the participant or LAR must return the original signed document on their first in person visit or by mail if there is no in person visit.
- If the signed consent form is mailed to the consent designee by the participant or LAR, The IRB-approved consent designee will sign their copy which they possess after the participant has acknowledged signature on their copy. Once the participants original copy is received the consent designee copies will be attached to make a single document.
- If the participant signed consent form is provided immediately by electronic format (emailed, faxed or photo/scanned to text, once received, the IRB-approved consent designee signs, dates/times this informed consent document.

We will provide participants with password protected ZOOM links for all meetings.

We will distribute flyers to the Maryland AARP, senior housing residents, African American hair salons, and on Facebook local group and organization sites. A study team member will obtain necessary permission from administrative staff at all locations before any flyers are distributed via postal mail or email.

We will randomize participants to each group with the following process. 1) Once we find potentially interested participants through the above referral sources, we will telephone screen for eligibility and explain study procedures. 2) If eligible by phone, the research assistant will re-screen, re-explain the study, obtain consent (via DocuSign or hard copy ), and conduct the baseline data collection. 4) If participants qualify for the study after this visit, within 48 hours of the baseline interview, we will randomize using a computer-based assignment scheme and communicate the assignment to participants by letter. An employee of the Johns Hopkins Center of Innovative Care in Aging will be unblinded and will complete the randomization for the project. 5) The person assigned to randomize will inform the nurses of the participants' group (intervention or control). 7) The nurses will contact the participant within one week to schedule the first appointment.

The wait list control group will have data collectors schedule a Zoom video visit with them. The same data will be collected for the intervention group. Participants in the wait list control group will not start the DAPPER intervention until the intervention group has completed the study. The wait list control group will receive monthly phone calls to confirm contact information.

**Data Collectors:** The data collectors have been trained to obtain baseline and outcome measures of each participant. The data collectors will collect baseline and outcome data and are responsible for teaching the participants how to collect saliva samples. The data collectors will call participants to schedule the first Zoom video call. The data collector will call/log on at the mutually agreed time. The data collector will complete the questionnaire booklet with the participant and complete the frailty phenotype measurements

with the participant. If the participants meets the criteria for frailty, pain, and depression, enrollment in the study will continue. Upon completion of the nurses' visits, the data collectors will schedule a final visit with participants.

**Research Nurses:** An RN is the appropriate professional to conduct the visits because of the training in assessment skills, and knowledge base in physiology, medications, and patient education in pain and depressive symptoms. The nurses have been trained on the protocol. The nurses will call the participants to schedule the first visit. The nurses will meet with participants via Zoom video calls during a mutually agreed upon time. The nurses will work with participants to set goals surrounding pain and depressive symptoms. The goals will be participant driven and documented by the nurse. The nurse will then work with the participant to identify strategies to work on three goals.

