### **1. Abstract**

Older African American women experience disproportionate rates of chronic conditions in comparison to other groups. Pain, depressive symptoms, and frailty often co-occur in African American women aging with chronic conditions and this combination can lead to disability and poor quality of life. Addressing pain and depressive symptoms may improve or delay the progression to frailty. To our knowledge there is little work being done in this population to address both pain and depression. The Depression and Pain Perseverance through Empowered Recovery (DAPPER) program is person directed and will consist of 8 nurse visits during which the nurse assesses each participant for pain, depression, and frailty, then implements a manualized individually tailored intervention. The data collection visits, and nurse visits will take virtually. We propose a pilot trial that is a wait list randomized control pilot to test the acceptability and obtain a preliminary effect size for the intervention. We will recruit 64 ( $\geq$ age 50) African American women who report pain intensity of 3 or higher that interferes with their activities, depressive symptoms lasting more than two weeks, are pre frail or frail, and live in the community/are not institutionalized. The sample will be recruited through the PI's previous study, community recruitment flyers distributed virtually, and word of mouth campaigns. Participants will be randomized into either the intervention or the wait list control group. Once the intervention group has completed their visits, the wait list control group will begin their visits. All participants will be offered the same information and format of nurse visits. The nurses will systematically tailor the content of the visits to the participants' risk profile and goals based on protocols. All participants will be assessed at the start of the study, at 12 weeks, and 24 weeks. The primary outcomes will be pain, depressive symptoms, and frailty status. Other endpoints include goal attainment, stress (cytokines), self-report, self-efficacy, and communication with health care providers. We will also examine the acceptability of the intervention using intervention compliance and one-on-one qualitative interviews. This study will offer either virtual or in person visits based on the preference of the participants.

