### **2. Objectives**

The aims of this pilot project are to 1) test the Depression and Pain Perseverance through Empowered Recovery (DAPPER) program for feasibility and acceptability. Specifically, we will 1) test the effect size of DAPPER on pain and depressive symptoms from baseline to 12 weeks (compare intervention to wait list control group) and then at 24 weeks to compare the intervention group to wait list control group once again, 2) estimate preliminary effect sizes for DAPPER in reduction of frailty, and 3) measure effect sizes and feasibility of measuring cytokines.

This study is being supported through funding from the Harold Amos Medical Faculty Program and the Johns Hopkins Older Adults Independence Pepper Center.

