**Self- Management Interventions:** Self-Management interventions have been successful at addressing conditions such as depression and physical function among older adults. Self-management is defined as the tasks or strategies that are conducted within the living environment that promote health by addressing conditions or symptoms across five core areas: problem solving, decision making, resource utilization, partnerships with healthcare providers, and taking action. A self-management behavioral activation intervention that has effectively treated depressive symptoms in older African Americans is the Get Busy Get Better/Beat the Blues intervention (NIMH, RO1 MH 079814, PI :[name]). Get Busy Get Better included 208 community dwelling African Americans with depressive symptoms in Philadelphia. The intervention included up to ten visits by licensed social workers over 4 months. The visits included ongoing education about depression and related treatment for depression. The participants did set their own goals (decision making) and the education and treatment (problem solving) assisted them with achieving these goals. Another intervention, the Community Aging in Place, Advancing Better Living for Elders (CAPABLE) study (NIH, R01-AG040100, PI: [name]), is a person directed tailored program in which participants set their own goals (decision making) and work with occupational therapists and nurses (partnerships with healthcare providers) to use individually tailored strategies (problem solving) to meet their self-selected goals. The participants select goals from areas related to physical function as well as pain management, depression, falls, and communication with health care providers. CAPABLE shows improvement in physical function, pain, depression, and disability outcomes. CAPABLE has been replicated in 28 sites in 14 state including statewide in Massachusetts. To our knowledge, there have been no tailored self-management person directed interventions that address a group of conditions such as pain, depressive symptoms, and frailty among older African American women.

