### Approach

**4.a Theoretical Framework:** Self-regulation theory is the theoretical framework for this study. Self-regulation theory involves two tenets: 1) participants manage their response based on their experiences (experiences with pain, depression, and frailty treatments) and knowledge of an event and 2) participants' goals are to maintain comfort and decrease the negative effects of an illness (pain depression and/or frailty) on their lives. The intervention is participant centered and participant driven. This means that the participants' experiences and existing knowledge about pain, depressive symptoms, and frailty will drive the goals that they set. For example, a participant may have experienced pain, depression symptoms, and frailty; she is no longer able to go work in her garden. Her goal may be to be able to garden again. This would provide comfort, decrease the effects of these three conditions, and potentially improve her symptoms.

**Design overview of the study:** The design of the study is outlined in the above figure. The outcomes will determine effect sizes on the intervention's effect on pain and depressive symptoms. Outcomes will be measured at 12 weeks (compare intervention and wait list control group) and at 24 weeks (look at outcomes for wait list control group and outcomes over time for intervention group). Goal attainment will be measured at 12 weeks and 24 weeks. At 24 weeks, we will also conduct virtual semi-structured one on one individual interviews with participants to determine feasibility and acceptability.

The intervention group (n=30) will start the study and will receive eight nurse visits that will be focused on decreasing pain, depressive symptoms, and meeting participant selected goals set in these areas. The wait list control group will receive monthly calls by a study team member to ensure their contact information

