After the informed consent process is completed, the IRB approved study team member files the consent document in the research record, including a note confirming the consent process. The data collector will verify if the participant has any questions regarding the consent form and verify the participant understands the consent form. The data collector will ensure that the participant reads the consent form and has a copy of the consent form. After the consent is completed, a formal assessment of outcomes will be done. The data collector will explain the process of saliva sample collection to the participant. We will not collect saliva samples from participants outside of Maryland. A kit will be dropped off to the participants with non-contact either at their door or given to front office. We will call and confirm participants receive the kits. The participants will be asked to store samples in their home refrigerator. If there is not a working refrigerator, the participants will be provided with a cooler and ice packs that will be replaced over the two days. When the participant is ready for the saliva sample to be picked up, they will notify us, and it will be picked up using protective gear (gown, gloves, and mask) without contact with participants and stored in the Johns Hopkins School of Nursing lab.

**Final Data Collection Visit:** At this visit, the data collector will enact the same protocol as at baseline.

**Saliva Sample Visits:** A member of the research staff will contact the participants to ask them a good time to pick up samples. The research staff member will arrive to participants home to pick up samples. Personnel picking up the samples will notify participants when they are arriving, and participants will place the sample outside the front door once the staff member pulls up or walks up to their home location. The staff member will label the specimens and take them directly to the Johns Hopkins School of Nursing refrigerator. Please see specifics below (laboratory studies) for further information about the collection and storage process of the saliva samples.

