**Table 1- Instruments Measuring Main Outcome Variables**

Outcomes	Instruments
Cognition (see inclusion/exclusion criteria)	Short Portable Mini Mental Status Exam 
Depressive Symptoms	Patient Health Questionnaire 9 and Patient Reported Health Outcomes (PROMIS) 57 
Pain	PROMIS Pain Interference, Pain Intensity and Pain Behavior 
Communication	Patients' Reaction Assessment 
Comorbid Conditions	Charlson Comorbidity Index 
ADLS/IADLS	Katz 
Frailty	Frailty phenotype  Frail Scale  will be used to measure frailty.
Stress	Perceived Stress Scale 
Self-Efficacy	Coping and Self-Efficacy Scale 
Readiness to Change	Gitlin and Rose's Readiness to Change Rating System (Gitlin & Rose, )
Social Network Scale	Lubben Social Network Scale
IL6	Saliva Sample
TNF $\alpha$	Saliva Sample
IL8	Saliva Sample
IL-1 $\beta$	Saliva Sample
Goal Attainment	Subjective Report

The following instruments and a demographic questionnaire (e.g. age, SES, and education) will be administered to the participants' pre- and post-intervention.

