#### **5. Study Statistics**

##### **Sample size calculation and analysis of aims**

**Sample size:** To calculate effect sizes for planning a definitive trial our sample size calculations were based on the need to pilot DAPPER for pain and depressive symptoms. We assume an attrition rate of 13% during the 16-week follow-up based on the CAPABLE trial. Based on these assumptions, an initial sample size of 64 participants (32 in the intervention group and 32 in wait list control) would yield 52 participants (25 intervention, 25 wait list control) after attrition. It is unlikely we will detect a significant difference between the groups due to small sample size and limited follow-up.

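### The visit procedures schedule the final data visit when the nurse visits end, which conflicts with the week 12 and week 24 assessments stated for all participants

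*Combined protocol and SAP*

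**What the plan says.** The protocol describes the outcome assessments in two ways.

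**By calendar.** Section 1 (Abstract) states: "All participants will be assessed at the start of the study, at 12 weeks, and 24 weeks". Section 2 (Objectives) sets out to "test the effect size of DAPPER on pain and depressive symptoms from baseline to 12 weeks", with a second between-arm comparison at 24 weeks. The design overview under Approach agrees: "Outcomes will be measured at 12 weeks (compare intervention and wait list control group) and at 24 weeks".

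**By completion of the nurse visits.** In the DAPPER Protocol, the paragraph on data collectors says: "Upon completion of the nurses' visits, the data collectors will schedule a final visit with participants". It gives no week and no window. The Visits section then describes Data Collection Visit One and a single Final Data Collection Visit, of which it says: "At this visit, the data collector will enact the same protocol as at baseline". The text under Table 1 has the instruments given "pre- and post-intervention". Biomarker Procedures takes saliva at the first and last data visits, and the data management paragraph names only final data collection after screening and the sessions. The wait-list paragraph provides a Zoom data visit but does not date it.

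**Analysis.** The analytic approach in section 5 fits GEE with time, group and their interaction, and interprets the effect size of that interaction. It presents this as intention-to-treat because non-completers' data are used. It adds a completers-only sensitivity analysis and promises to keep non-compliance separate from missing data.

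**The concern.** The aim is an effect size between arms at a common time after randomisation, with women who stop early included. The calendar schedule delivers that. The visit procedures, which are what data collectors will work from, do not clearly do so.

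Two things are at stake if the procedures are followed as written. First, the intervention arm's outcome clock runs on visit completion while the wait list's clock is undefined, so time since randomisation may differ by arm. Second, a woman who stops the nurse visits never reaches the event that prompts her final data visit, so the intervention arm's follow-up scores would come from finishers. GEE can use every score that was collected, but it cannot supply one that was never taken.

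**Working it through.** The plan gives no figure for assessment timing, so there is none to reproduce. The check compares the texts and then asks how far the two schedules could diverge.

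**1. Is the completion trigger an isolated phrase?** No. The Visits section, the text under Table 1, the saliva timing and the data management paragraph all fit a first-and-final scheme. Goal attainment shows the same split: weeks 12 and 24 in the design overview, nurse visits five and eight in the Outcomes section. No available text describes how a week-12 visit is carried out.

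**2. When would nurse visit 8 fall?** Let s be the week of the first nurse visit and g the gap between visits. Then visit 8 falls at week s + 7g.

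- The number of visits, eight, is from the Abstract.
- The randomisation steps allow 48 hours from baseline to randomisation and one week for the nurse to make contact. I take s = 0.3 to 2 weeks from baseline (assumption).
- The gap is not stated. I take g = 1 to 2 weeks (assumption).

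| Gap g (weeks) | s = 0.3 | s = 2 |
|---|---|---|
| 1 | 0.3 + 7 = 7.3 | 2 + 7 = 9 |
| 1.5 | 0.3 + 10.5 = 10.8 | 2 + 10.5 = 12.5 |
| 2 | 0.3 + 14 = 14.3 | 2 + 14 = 16 |

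Against week 12, the range runs from 12 − 7.3 = 4.7 weeks early to 16 − 12 = 4 weeks late, before any delay in booking the data visit.

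**3. How many women might miss the trigger?** The documents give no rate of stopping DAPPER; the 13% in section 5 is attrition, which is a different quantity. With 32 in the intervention arm (section 5) and an assumed 5% to 30% stopping, the count is 32 × 0.05 = 1.6 to 32 × 0.30 = 9.6, or about 2 to 10 women. With the arm size of 30 printed in the design overview it is 1.5 to 9.

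**4. What would that do to the estimate?** If a fraction p stop and their outcomes are worse than finishers' by d standard deviations, leaving them out overstates the arm's result by p × d. For illustration only: 0.20 × 0.5 = 0.10 SD and 0.30 × 0.5 = 0.15 SD. Both p and d are assumed, and the sign reverses if stoppers do better.

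**5. What happens to the section 5 analyses?** If early stoppers have baseline data only, the intervention arm's follow-up scores are largely the same in the intention-to-treat and completers-only analyses, so comparing the two says little. Non-compliance also cannot be separated from missing data when non-compliance itself removes the assessment.

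**The case against.** The strongest reply is that the protocol does set a calendar. Three sections name week 12, two of them as the between-arm comparison, and none makes it depend on finishing the nurse visits. The data collectors' sentence speaks of a final visit, not the only one, and first and last saliva visits leave room for one between them. Comparing arms at 12 weeks and then treating the wait list suggests that the eight visits were meant to fit about 12 weeks, in which case the two wordings nearly coincide. Section 5 plainly intends to have data from some non-finishers. The design figure could not be seen and the intervention manual is a separate document; either may give visit timing. Finally, this is a pilot that disclaims power: 0.10 to 0.15 SD is small beside a standard error of about √(2/25) = 0.28 SD at the plan's 25 per arm.

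Much of this stands, and it rules out several stronger readings that a reader might infer:

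- *That early stoppers have no assessment trigger anywhere.* This is true of the visit procedures read alone, not of the whole document.
- *That the wait list's score is taken after DAPPER, leaving no untreated week-12 comparator.* The wait list has its own data visit, not tied to nurse visits, and both Objectives and the design overview call for an intervention versus wait-list comparison at 12 weeks. That visit is undated, which is a smaller point.
- *That the intervention arm will be assessed late.* The parent programme's description, "The intervention included up to ten visits by licensed social workers over 4 months", would put visit 8 at about weeks 13 to 15.5 (17.3 weeks over 10 or 9 intervals; 1 + 7 × 1.73 = 13.1, 2 + 7 × 1.93 = 15.5). Nothing says that DAPPER keeps that pace, and early is as possible as late.
- *That section 5 sets a third clock.* The sentence "We assume an attrition rate of 13% during the 16-week follow-up based on the CAPABLE trial" may describe CAPABLE's own follow-up.

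What the reply does not remove is the conflict itself. An intention stated in the design sections does not tell a data collector to assess a woman who has stopped her visits, when the procedure says to schedule the final visit once the visits are complete. Nor does low power excuse a selection effect: the effect size is wanted for planning a definitive trial, and such a bias does not shrink with sample size.

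**Conclusion.** The protocol contains an unreconciled conflict between its stated assessment schedule and its visit procedures. The calendar schedule supports the effect-size aim; the procedures, followed as written, may not. They allow the arms to be assessed at different times from randomisation and contain no prompt to assess a woman who stops DAPPER early.

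The possible mismatch of 4 to 5 weeks either side of week 12 and the 2 to 10 untriggered women rest on assumed visit gaps and stopping rates. They show what the wording permits and do not predict what will happen. The documents do not allow the bias to be computed. The point still merits correction, because a week-12 score that was not collected cannot be recovered at analysis, and the intention-to-treat claim in section 5 depends on having it.

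**What to change.** In the data collectors' paragraph, the Final Data Collection Visit text and the sentence under Table 1, replace the completion trigger with data collection visits at 12 and 24 weeks from randomisation (or baseline; choose one and use it throughout). Apply this to both arms with one common window chosen by the sponsor, and state that the visits take place however many nurse visits have been completed.

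In addition:

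- describe the week-12 visit in the Visits section for both arms, and date the wait-list visit;
- confirm that each wait-list woman's week-12 assessment comes before her first nurse visit;
- record the number of nurse visits each woman has received by week 12, so that compliance can be analysed separately from missing data.

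The cost is protocol wording and a scheduling rule. No assessment is added beyond the three promised in the Abstract, and the number and content of the nurse visits do not change. The downside is that some women will be assessed at week 12 before their eighth visit; the recorded visit count lets the analysis show how many.
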